## GENERAL INFORMATION

Randomized clinical trial with a parallel observational arm comparing the effectiveness of surgical stabilization of rib fractures to usual care in trauma patients with severe thoracic trauma. Study will evaluate for differences in clinical metrics as well as patient-centered outcomes. Prospective enrollment over 18 months with a 6-month follow-up period is intended.

## ABSTRACT

**BACKGROUND:** Rib fractures are the most common injury in blunt thoracic trauma and are a major source of morbidity and mortality. In severe cases, usual care with pain medications is often insufficient to prevent respiratory failure, pneumonia, and tracheostomy. Additionally, patients may go on to have pain that far exceeds their hospitalization and limits their ability to return to work. Surgical stabilization of rib fractures (SSRF) is a promising intervention that may decrease morbidity and time to return to work.

**PROBLEM:** Few high-quality studies have been performed that compare SSRF to usual care. Of these, even fewer have considered patient-centered outcomes following discharge. Furthermore, SSRF is often performed late as salvage therapy rather than early as a preventative intervention.

**STRATEGY:** To address this gap in knowledge, we propose to perform a randomized trial with a parallel observational arm of blunt trauma patients with multiple rib fractures comparing the effectiveness of early SSRF to usual care on clinical and patient-centered outcomes. The primary endpoint is hospital length of stay. Secondary endpoints will include clinical outcomes (incidence of respiratory failure, pneumonia, tracheostomy, mortality) and patient-centered outcomes (health status and time to return to work).

## BACKGROUND INFORMATION

Approximately 350,000 people suffer rib fractures in the United States each year, with more than one-third requiring hospitalization. Severe chest trauma may result in prolonged mechanical ventilation, post-traumatic pneumonia, long-term disability, and death. Morbidity and mortality increase with each fractured rib, and an inflection point seen at six or more rib fractures. Usual care typically consists of breathing exercises and pain control, often including opioids. However, despite usual care, rib fracture patients are more physically disabled at 30 days post-injury than a reference group of chronically ill patients and lose 70 days of work or usual physical activity.

An alternative to usual care is surgical stabilization of rib fractures (SSRF). Surgical stabilization of fractures is a well-established tenet of orthopedic surgery that is proven to facilitate bone healing, decrease the mobility of fractures, decrease pain, and improve mechanical function. Decreasing the mobility of fractured ribs has been shown to improve pain in small studies, and it may decrease the consumption of opioid pain medications. However, because the SSRF literature is plagued by industry bias and low-quality studies, the indications for the procedure remain unclear and it is rarely performed.

Evidence for SSRF in Flail Segments: In three small, randomized trials of patients with flail segments (radiographic findings of  $\geq 3$  consecutive ribs with  $\geq 2$  fractures), SSRF has been shown to decrease the duration of mechanical ventilation, the incidence of pneumonia, the duration of intensive care, and overall medical costs. Similarly, recent systematic reviews and meta-analyses of these studies have supported the reduction in duration of mechanical ventilation, pneumonia, and tracheostomy. However, these trials and meta-analyses are limited by study heterogeneity, narrow inclusion criteria, and small sample sizes ( $n < 50$ ). For these reasons, SSRF has not been widely adopted in the flail segment population.

Evidence for SSRF in Non-Flail Chest Wall Injury: Most patients with severe chest trauma do not have a flail segment. Rather, patients may have multiple consecutive fractures or fractures with displaced fragments. Although the use of SSRF for non-flail chest indications is an attractive option, only low-quality evidence exists to support its use. This paucity of evidence is further highlighted by a recent systematic review in which only three studies of SSRF in non-flail chest (all retrospective reviews) could be identified.

In addition to a paucity of evidence for traditional outcome metrics, no high-quality trials have evaluated the effect of SSRF on patient-centered outcomes, such as health status and quality of life. To address these gaps in knowledge, this proposal aims to determine the comparative effectiveness of early SSRF to usual care on traditional outcome metrics and patient-centered outcomes, such as long-term health status and quality of life in blunt trauma patients suffering multiple rib fractures.

## GOAL AND SPECIFIC AIMS

Aim 1: Compare the effectiveness of SSRF to usual care alone on traditional clinical metrics and patient-centered outcomes.

Aim 2: Evaluate for heterogeneity of treatment effect in high-risk subgroups.

Aim 3: Determine the impact of multiple rib fractures on post-discharge health status and time to return to work or usual physical activity.

## HYPOTHESIS

Patients with severe chest trauma who undergo SSRF will have decreased rates of opioid consumption as measured in morphine milligram equivalents per day. Patients with severe chest trauma who undergo SSRF will also have improved health status (as measured by the EuroQOL-5D-5L) at 30 days and 3 months, earlier return to work or normal physical activity, and decreased time from injury to resolution of chest wall pain.

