### Secondary Outcomes (Clinical Metrics):

- Mortality
- Incidence of respiratory failure requiring mechanical ventilation > 24 hours
- Incidence of tracheostomy
- Inpatient incidence of pneumonia
  - >10,000 cfu/mL on bronchioalveolar lavage -or-
  - Clinical diagnosis of pneumonia with subsequent antibiotic treatment
- Utilization of regional anesthesia (binary outcome)
- Opioid usage (continuous and binary)
- Lengths of stay
  - Hospital-free days (= 30 minus number of hospital days; in-hospital death = 0)
  - Ventilator-free days (= 30 minus number of ventilator days; in-hospital death = 0)

- ICU-free days (= 30 minus number of intensive care unit days; in-hospital death = 0)
- Re-intervention rates for surgical complications, including bleeding, seroma, and surgical site infection

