### Randomization:

Eligible subjects who have consented to participate will be randomized into one of two groups: 1) Control arm or 2) Intervention arm. The two arms are described in detail below. A 1:1 allocation ratio using a permuted block design of 4 or 6 will be used to ensure equal number of patients in each group. Randomization will be performed using the randomization module in REDCap and stratified by unit of admission.

Control Arm: Control patients will receive usual care per our established institutional guidelines, consisting of pulmonary toilet, lung volume expansion exercises, and a multimodal approach to oral pain medication management. For severe pain not responding to oral therapy, intravenous narcotics, lidocaine, or ketamine may be added. Regional analgesia techniques such as epidural analgesia, paravertebral analgesia, and intercostal nerve blockade may also be considered. The pain medication regimen is deescalated as pulmonary status and pain control allow.

(<https://med.uth.edu/surgery/files/2017/06/Chest-Management-of-Multiple-Rib-Fractures-2013.pdf>)

For patients who fail all of these therapies and desire to proceed with SSRF, the procedure may be offered late, as salvage therapy.

Intervention Arm: The intervention will consist of early surgical stabilization of the fractured ribs plus usual care. If randomized to SSRF, the procedure should occur as early as possible (given the patient clinical status and need for more emergent procedures), ideally within the first 72 hours of hospital admission. Since stabilization of all fractures may not be possible due to anatomic exposure (e.g., the first, second, and third ribs may be difficult to access due to their location), the surgery must stabilize at least one true rib (ribs 1-7). Stabilization of the true ribs is considered more critical due to their greater contribution to chest wall volume and mechanical respiratory function.

Observation Arm: Patients refusing consent to randomization will be invited to participate in the observational arm. Patients selecting this option will be asked to complete the same assessments as the randomized groups.

Equipment: In order to maintain a pragmatic approach, surgical stabilization will be performed using any commercially available internal rib fixation system, at the discretion of the operating surgeon.

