### Data Collection

The clinical research staff will follow the subjects throughout their hospitalization (or up to 30 days, whichever comes first) for complications such as surgical site infections, pneumonia, need for reoperative procedures and other complications commonly associated with rib fractures.

The data will be reviewed and entered into the UT Redcap database. Each subject will be assigned a study specific number. The subject's medical record and the MHH-TMC trauma registry will be utilized for data collection purposes. Data will be collected until discharge or 30 days (whichever occurs first) and questionnaires will be conducted up to 6 months post ED admission.

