### Sample Size Calculation

We expect to enroll 150-250 total patients. We calculated the effect size we will be able to detect in hospital LOS, assuming a median LOS of 10 days (IQR 6-15) in the control group and two-sided alpha of 0.05. A sample size of 150 patients (75 per group) will provide 85% power to detect a difference of 3 days (*i.e.*, median LOS of 7 days in intervention group). With a sample size of 250 patients, we will have 89% power to detect a difference of 2.5 days in hospital LOS.

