#### Appendix B. List of Data Elements to be Collected

Study number

Gender (male/female)

Age

Race (white, black, Hispanic, Asian, other, unknown)

Trauma type (blunt/penetrating)

Mechanism (MVC, MCC, fall, auto pedestrian, ATV, assault, crush, GSW, stab, other)

Date/time of injury

PH vital signs

Transfer? (yes/no)

ED arrival date/time

ED vitals

ED CBC

ED BMP

ED rTEG

ED lactate

ED base excess

Unit of admission

Randomization group (SSRF/usual care)

R 1st rib fx?

Segmental?

Displaced?

R 2nd rib fx?

Segmental?

Displaced?

R 3rd rib fx?

Segmental?

Displaced?

R 4th rib fx?

Segmental?

Displaced?

R 5th rib fx?

Segmental?

Displaced?

R 6th rib fx?

Segmental?

Displaced?

R 7th rib fx?

Segmental?

Displaced?

L 1st rib fx?

Segmental?

Displaced?

L 2nd rib fx?

Segmental?

Displaced?

L 3rd rib fx?

Segmental?

Displaced?

L 4th rib fx?

Segmental?

Displaced?

L 5th rib fx?

Segmental?

Displaced?

L 6th rib fx?

Segmental?

Displaced?

L 7th rib fx?

Segmental?

Displaced?

Radiographic flail segment? (yes/no)

Flail chest? (yes/no)

Right clavicle fx? (yes/no)

Left clavicle fx? (yes/no)

Right scapula fx? (yes/no)

Left scapula fx? (yes/no)

Mechanical ventilation immediately prior to SSRF? (yes/no)

Tracheostomy prior to SSRF? (yes/no)

Clinical suspicion of PNA prior to SSRF? (yes/no)

Chest tube prior to SSRF? (yes/no)

Date/time of SSRF

Time from admission to SSRF (hours)

Procedure time (min)

Hardware system (Synthes/KLS Martin)

Right ribs stabilized by SSRF

1 (yes/no)

2 (yes/no)

3 (yes/no)

...

Left ribs stabilized by SSRF

1 (yes/no)

2 (yes/no)

3 (yes/no)

...

VATS? (yes/no)

Thoracotomy? (yes/no)

w-RTS

ISS

AIS head/neck

AIS face

AIS chest

AIS abdomen

AIS extremity

AIS external

Regional analgesia for rib fxs? (yes/no)

If yes, what kind? (epidural, paravertebral, intercostal, serratus plane, other)

Post-SSRF PNA? (yes/no)

Post-SSRF hardware infection? (yes/no)

Post-SSRF seroma requiring intervention? (yes/no)

Post-SSRF hematoma requiring intervention? (yes/no)

Post-SSRF hardware failure? (yes/no)

Post-SSRF need for hardware removal for any reason? (yes/no)

Post-SSRF SSI? (yes/no)

Superficial? (yes/no)

Deep? (yes/no)

Organ space? (yes/no)

DVT? (yes/no)

PE? (yes/no)

Discharge date/time

Discharge disposition (home, rehab, SNF, LTAC, transfer to other hospital, level 1 psych, morgue, other)

Total opioid use (MME)

MME/day

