Opioid prescription at discharge? (yes/no)

Tramadol prescription at discharge? (yes/no)

Ventilator days

ICU days

Hospital days

Did the patient survive to 1 month? (yes/no)  
Was the patient able to answer questions at 1 month? (yes/no)  
Did the patient consent to be asked questions at 1 month? (yes/no)

Did the patient survive to 3 months? (yes/no)  
Was the patient able to answer questions at 3 months? (yes/no)  
Did the patient consent to be asked questions at 3 months? (yes/no)

Did the patient survive to 6 months? (yes/no)  
Was the patient able to answer questions at 6 months? (yes/no)  
Did the patient consent to be asked questions at 6 months? (yes/no)

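### MME per day has no stated window or denominator; if it means total MME over days of stay and use tapers, a shorter SSRF stay raises it with identical daily use

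*Combined protocol and SAP*

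**What the plan says.** The Hypothesis section opens with opioid use, expecting "decreased rates of opioid consumption as measured in morphine milligram equivalents per day". Under Secondary Outcomes (Clinical Metrics) the outcome is only "Opioid usage (continuous and binary", with no unit, window or denominator.

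For the inpatient period, Appendix B lists a single total in MME, a single MME/day value and "Hospital days". No day-by-day MME is listed. It also has two yes/no items on opioid and tramadol prescription at discharge. Under Data Collection, in-hospital capture ends at discharge or day 30, whichever is earlier.

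Length of stay is the primary outcome. The Sample Size Calculation works by "assuming a median LOS of 10 days (IQR 6-15) in the control group and two-sided alpha of 0.05", against a "median LOS of 7 days in intervention group". On the course of opioid use, the control-arm description under Randomization says "The pain medication regimen is deescalated as pulmonary status and pain control allow". The intervention arm receives usual care in addition to surgery, so this applies to both arms. Frequentist Analysis applies generalized linear models with treatment and unit of admission to all outcomes. It says nothing specific about opioid use or about stays of unequal length.

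**The concern.** The plan does not say over which days MME per day is averaged. The elements collected point to total MME over days of stay, although this is an inference. On that reading the denominator is the primary outcome, and the trial is sized to see it fall.

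If use is highest early and then tapers, the patient who goes home sooner is averaged over the heavier days only. The SSRF average can then exceed the control average with no difference on any given day, which works against the plan's own opioid hypothesis. The whole-stay total has the opposite fault: it falls because counting stops at discharge. The two inpatient measures can therefore disagree for reasons unrelated to opioid need, and no rule says which one governs. If only one total and one average per patient are stored, this cannot be corrected later without going back to the records.

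**Working it through.** The plan states no MME mean, SD, effect size or power, so there is no figure of its own to reproduce. The check asks what whole-stay MME/day shows when both arms use the same amount on every day.

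**Inputs.** Stays of 10 days (control) and 7 days (SSRF) come from the Sample Size Calculation. Day-1 use is set to 100, an arbitrary scale that cancels in ratios. The daily proportional fall r is an assumption, because the plan describes de-escalation without a rate.

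**Formula.** With use on day d equal to 100(1−r)^(d−1), the average over L days is A(L) = 100·[1−(1−r)^L]/(r·L) and the total is L·A(L).

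Example, r = 0.10: A(10) = 100·(1−0.9^10)/1.0 = 65.1 and A(7) = 100·(1−0.9^7)/0.7 = 74.5. The ratio is 74.5/65.1 = 1.14. The totals are 651 and 522, ratio 0.80.

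| Daily change | Control, 10 d | SSRF, 7 d | MME/day ratio | Total MME ratio |
|---|---|---|---|---|
| flat | 100.0 | 100.0 | 1.00 | 0.70 |
| −5% | 80.3 | 86.2 | 1.07 | 0.75 |
| −10% | 65.1 | 74.5 | 1.14 | 0.80 |
| −20% | 44.6 | 56.4 | 1.26 | 0.89 |
| +5% | 125.8 | 116.3 | 0.92 | 0.65 |

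The total ratio is 0.7 times the average ratio.

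**Whole distributions instead of two medians.** The stated IQR of 6 to 15 gives a log-SD of ln(15/6)/(2×0.6745) = 0.679. With lognormal stays at medians 10 and 7, capped at 30 days, the MME/day ratios are 1.07, 1.13 and 1.21 for falls of 5%, 10% and 20%. They are 1.00 for flat use and 0.91 for a 5% rise. The result is therefore not an artefact of comparing medians.

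**What could be hidden.** The true proportional reduction in daily use that would just cancel the inflation is 1 − A(10)/A(7): 6.9%, 12.6% and 20.9% at falls of 5%, 10% and 20%.

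**Common window.** Averaged over days 1-7 for everyone, identical daily use gives a ratio of 1.00 for every curve.

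**The case against.** A reader might infer that the plan defines MME/day as a whole-stay average, that this average must rise when SSRF shortens the stay, and that the plan collects nothing else on opioids. The documents support none of these. The denominator is unstated. The rise needs falling use: it is absent with flat use and reversed with rising use. The two discharge prescription items are binary measures that do not depend on days of stay. The shorter stay is also the sample-size assumption for the primary outcome; the Hypothesis section does not mention it.

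The strongest point on the other side is that de-escalation is tied to pulmonary status and pain control, not to calendar day. If SSRF speeds recovery, taper and discharge may both come earlier. Suppose the control falls 10% per day and the SSRF taper is compressed by 10/7. The SSRF daily factor is 0.9^(10/7) = 0.860, its 7-day average is 100·(1−0.9^10)/(7×0.140) = 66.6, and the ratio to control is 66.6/65.1 = 1.02. The spurious rise nearly disappears, so the 7% to 26% range does not hold in general. The measure would still report near-equality in that case, although SSRF use over days 1-7 is lower by 1 − 66.6/74.5 = 11%.

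A fixed window also has a weakness, because patients sent home early contribute fewer days. Under the lognormal stays above, with days counted from admission, Φ(ln(5/7)/0.679) = 31% of SSRF and Φ(ln(5/10)/0.679) = 15% of control patients have stays shorter than 5 days. For 7 days the figures are 50% and Φ(ln(7/10)/0.679) = 30%. This loss is differential and related to recovery. It stands as a reason to prespecify a rule, not as a reason to keep the whole-stay average.

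**Conclusion.** The concern holds as a conditional one. The plan leaves the window and denominator of its opioid measure undefined, and the natural reading of the collected elements makes the measure depend on length of stay.

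On that reading, with stays of 7 and 10 days, identical daily use and an assumed calendar-day fall of 5% to 20%, MME/day is about 7% to 26% higher under SSRF, while total MME is about 11% to 25% lower. The direction rests on tapering, which the plan describes. The size rests on a taper rate that the plan does not give.

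This affects a secondary outcome. The primary analysis of length of stay and its sample size are untouched. It still deserves correction, because opioid use is the first hypothesis stated and the planned model does not remove the distortion.

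**What to change.** Define the inpatient opioid outcome over one common window with a single time origin, randomisation. Make it long enough to include post-operative days, given that the plan aims for surgery within 72 hours of admission; days 1-7 is one example. Record MME for each inpatient day in the window from the medication record. Compare like days with the mixed model in Frequentist Analysis, using treatment, day and unit of admission. That section names center as a covariate, but the trial has a single center.

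Prespecify how days after discharge and deaths are handled. Add a sensitivity analysis, because earlier discharge is expected in the SSRF arm. Matching days reduces the problem but need not remove it: in one simulation with a 10% daily fall and discharge linked to opioid need, the distortion went from about 15% for the whole-stay average to 0-5% over days 1-5. A longer window brings in more post-operative days but also more discharged patients.

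Report whole-stay MME/day (with its denominator stated) and total MME as descriptive. The discharge prescription items can stay as they are.

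The cost is up to seven daily values per patient from a record already in use, plus wording in the outcome and analysis sections. The drawback is fewer observed days for patients discharged early.

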## STUDY DESIGN

Single center, pragmatic, prospective, randomized clinical trial with a parallel observational arm to compare usual care alone to usual care plus early surgical stabilization of rib fractures. Screening will occur at admission. Randomization will occur after informed consent has been obtained. A 1:1 allocation ratio using a permuted block design of 4 or 6 will be used to ensure equal number of patients in each group. Randomization will be performed using the randomization module in REDCap and stratified by unit of admission. If randomized to SSRF, the procedure should occur as early as possible after admission (given competing/concomitant injuries), ideally within 72 hours. Study enrollment will occur over 18 months. Total study duration including follow-up = 24 months.

### Primary Outcome:

- Hospital length of stay (days)

### Secondary Outcomes (Clinical Metrics):

- Mortality
- Incidence of respiratory failure requiring mechanical ventilation > 24 hours
- Incidence of tracheostomy
- Inpatient incidence of pneumonia
  - >10,000 cfu/mL on bronchioalveolar lavage -or-
  - Clinical diagnosis of pneumonia with subsequent antibiotic treatment
- Utilization of regional anesthesia (binary outcome)
- Opioid usage (continuous and binary)
- Lengths of stay
  - Hospital-free days (= 30 minus number of hospital days; in-hospital death = 0)
  - Ventilator-free days (= 30 minus number of ventilator days; in-hospital death = 0)

- ICU-free days (= 30 minus number of intensive care unit days; in-hospital death = 0)
- Re-intervention rates for surgical complications, including bleeding, seroma, and surgical site infection

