**Exclusion Criteria:**

- Age  $< 16$  years
- Severe traumatic brain injury (best resuscitated GCS  $\leq 8$  as measured at 24h)
- Spinal cord injury
- Pre-existing congestive heart failure or oxygen-dependent pulmonary disease
- Any reason for which SSRF could not occur within 72 hours of admission

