### Frequentist Analysis

Generalized linear models (GLMs) will be used to analyze all outcomes and will include treatment group and unit of admission (stratifying variable) as covariates. For LOS outcomes, negative binomial or zero-inflated negative binomial (for outcomes with large number of zeros; *e.g.*, ventilator days, ICU days) regression models will be used. Binary outcomes will be analyzed with log binomial regression models to estimate relative risks (RRs). For longitudinal outcomes, we will use mixed models including treatment group, time, and center as covariates and a random intercept (and slope if needed) for subject. We will report RRs or group differences and 95% confidence intervals for all outcomes.

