## **ETHICS**

Written informed consent will be obtained from each patient prior to enrollment. In the event, the patient is unable to provide informed consent, the LAR or family member will be approached to provide consent for the patient. An assent form will be provided to those subjects 16 and 17 years of age. A member of the study team will discuss the trial details to the patient and/or LAR/family member and will allow them time to make a decision regarding participation.

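### The respiratory-failure outcome has no time origin and no rule for patients already ventilated at randomisation, so its relative risk may be attenuated toward 1

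*Combined protocol and SAP*

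**What the plan says.** Secondary Outcomes (Clinical Metrics) gives the outcome as "Incidence of respiratory failure requiring mechanical ventilation > 24 hours". It states no time origin and no rule for ventilation that is already under way at randomisation.

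Ventilated patients can be in the trial. None of the five Exclusion Criteria concerns ventilation at enrolment. The nearest is "Pre-existing congestive heart failure or oxygen-dependent pulmonary disease", which is about chronic disease. Ethics provides that if "the patient is unable to provide informed consent, the LAR or family member will be approached", so a sedated patient can be enrolled. Another exclusion, severe brain injury, uses a coma score "as measured at 24h".

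Appendix B expects some ventilated patients, since it asks "Mechanical ventilation immediately prior to SSRF? (yes/no". That item is tied to surgery and has no counterpart at randomisation for usual care. Otherwise ventilation appears only as a total, "Ventilator days", with no intubation or extubation times.

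Frequentist Analysis says "Binary outcomes will be analyzed with log binomial regression models to estimate relative risks (RRs", with treatment group and unit of admission as the only covariates. Statistics makes intention to treat the main analysis.

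**The concern.** The Abstract presents early surgery as prevention, observing that "SSRF is often performed late as salvage therapy rather than early as a preventative intervention". A patient ventilated since arrival may pass 24 hours before randomisation, or after randomisation but before an operation that may come as late as about 72 hours after admission. Surgery cannot prevent either event. As written, nothing stops such patients from being counted.

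If their share is similar in the two arms, these events add the same amount to both risks and say nothing about treatment. A real preventive effect would then look smaller on the planned relative-risk scale. The same dilution would carry into the Bayesian probability of benefit, because that analysis uses the same models.

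**Working it through.** **The plan's own figures.** No event rate, effect size or power is stated for respiratory failure. The only power figures are for hospital length of stay: 85% (150 patients, 3 days) and 89% (250 patients, 2.5 days). A gamma fit to the stated median of 10 and IQR of 6–15 gives mean 11.35 and shape 2.51. Used in a negative binomial Wald test with rate ratios 0.70 and 0.75, it gives 86.7% and 89.5%, close to the stated values. Nothing below depends on them.

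**Inputs.** All are assumptions, because the documents give none:
- v: share ventilated at randomisation
- c: control risk of new ventilation over 24 hours among the rest
- R: true relative risk for new events, set to 0.50

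**Formula, if every patient in v counts in both arms.**
Observed RR = [v + (1−v)·c·R] / [v + (1−v)·c].
This equals w·1 + (1−w)·R, with w = v / [v + (1−v)·c], the share of control-arm events that were already fixed. When that share is equal across arms, the observed value always lies between R and 1.

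| v | c = 15% | c = 25% |
|---|---|---|
| 10% | 0.1675/0.235 = 0.71 | 0.2125/0.325 = 0.65 |
| 20% | 0.26/0.32 = 0.81 | 0.30/0.40 = 0.75 |
| 30% | 0.3525/0.405 = 0.87 | 0.3875/0.475 = 0.82 |

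Over a wider grid (c 10–30%, v 5–30%), a true 0.50 appears as 0.58–0.91 and a true 0.70 as 0.75–0.94.

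**Relaxing the worst case.** Let f0 (control) and f1 (surgery) be the shares of already-ventilated patients who pass 24 hours. Take v = 20%, c = 20%, R = 0.50:
- f0 = f1 = 100%: 0.28/0.36 = 0.78
- f0 = f1 = 80%: 0.24/0.32 = 0.75
- f0 = f1 = 60%: 0.20/0.28 = 0.71
- f0 = 90%, f1 = 80%: 0.24/0.34 = 0.71
- f0 = 80%, f1 = 40%: 0.16/0.32 = 0.50, no dilution

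**Absolute scale.** The risk difference shrinks only by the factor (1−v). In this example it goes from 10 to 8 points.

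**Power (normal approximation, two-sided 0.05).** With the same inputs and all already-ventilated patients counted, the all-patient comparison of 36% with 28% has 18% power at 75 per arm and 27% at 125 per arm. Restricting to the 80% not ventilated (60 or 100 per arm), the comparison of 20% with 10% has 33% and 51%. Power is low either way, but the smaller denominator does not lower it here.

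**Can the listed fields separate the events?** The pre-surgery item is not asked of a control who has no operation. For a control who later has salvage surgery it describes a late time point. Even in the surgical arm it gives status just before the operation, not at randomisation. Total ventilator days cannot be divided at randomisation.

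**The case against.** The wording can be read more favourably. Incidence may mean new onset, and respiratory failure requiring ventilation is not the same as any ventilation, so intubation for an operation or for airway protection is not automatically an event. This stands as a reading, and the text is ambiguous rather than plainly wrong. But no sentence adopts that rule, and the listed fields could not apply it evenly.

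A reader might infer from the 24-hour coma score that eligibility always waits a day, so that every patient ventilated at randomisation has already met the outcome whatever the arm. The documents do not support this. The criterion concerns severe brain injury only; screening is at admission, randomisation follows consent, and no randomisation time is fixed. A patient randomised earlier may still be extubated before 24 hours. Background Information cites small flail-segment trials in which surgery shortened ventilation, so the share could also differ by arm.

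A reader might also infer that the events cannot be separated in controls. That goes too far: the medical record and trauma registry are named data sources and may hold the times. Clinicians and research staff are unblinded, however, so the rule is better set in advance than applied to charts later.

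Stratifying and adjusting by unit of admission, with subgroups by unit, may gather ventilated patients in one stratum. The units are not defined, and those events still count.

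Finally, the all-patient intention-to-treat relative risk is a legitimate pragmatic quantity, and restriction answers a different question. Respiratory failure is a secondary outcome that the Hypothesis section does not mention. Both points stand and limit the weight of the concern.

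**Conclusion.** The concern holds as an under-specified secondary outcome with a predictable direction of error. Ventilation that began before randomisation can count as an event, and to the extent that the share doing so is similar across arms, the relative risk is attenuated toward 1. The direction needs no assumed figure beyond that similarity.

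The size cannot be fixed from the documents. The illustrative range of about 0.65–0.87 for a true 0.50 rests on an assumed 15–25% control risk, 10–30% ventilated at randomisation, and all of those counting as events. Attenuation is smaller if some are extubated before 24 hours, and it vanishes only if surgery reduces their share as strongly as it reduces new events. The definition of the primary outcome and its stated power are not affected.

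**What to change.** - Record for every arm whether the patient is mechanically ventilated at randomisation (yes/no), with ventilation start and stop dates and times.
- Define the outcome as ventilation for more than 24 hours that starts after randomisation, among patients not ventilated at randomisation. Because status is fixed before allocation, the comparison within that subset remains randomised.
- Report the all-patient version as supportive, and let ventilator-free days, already a listed outcome, describe those ventilated at randomisation.
- Optionally, prespecify the baseline item as a covariate in the length-of-stay and free-day models. This is for precision only and is not needed to repair this outcome.

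The cost is one baseline item with its associated times, a sentence in the outcome list, and a smaller denominator for this one outcome (for example 60 rather than 75 per arm if 20% are ventilated). The item should be collected prospectively.
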